### 9.2.1.1 Analyses of Primary Endpoint

The primary endpoint is ORR.

**Objective Response Rate (ORR):** A patient will be considered to have achieved an objective response (OR) if the patient has a complete response (CR) or partial response (PR) according to RECIST version 1.1 (4) definitions. Otherwise, the patient will be considered as non-responder in the ORR analysis. ORR will be estimated by dividing the number of patients with objective response (CR or PR) by the **Efficacy** population ("response rate").

$$\text{Objective Response Rate} = \frac{\text{Number of CRs + PRs}}{\text{Efficacy Population}}$$

The ORR will be reported, including a 95% confidence interval using the Clopper-Pearson method (5).

These analyses will be conducted at a two-sided 0.05 level of significance.

The number of responders needed at the end of stage 2 to reject the null hypothesis is at least 14 responders.

Additional sensitivity analyses will be done with the ITT population. For the analysis in the ITT population, patients with inadequate data for tumour assessment (e.g., no baseline assessment or no follow up assessments) will be considered as non-responders in the ORR analysis.

In addition, the best objective response (BOR) for each patient will be summarized.

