8.1. Determination of Sample Size

8.1.1. Sample Size Determination

We have set the null hypothesis (H0) that ORR will be 30% (ORR achieved by TN patients treated with gemcitabine plus carboplatin¹) versus the alternative hypothesis (H1) that ORR will be 54% (ORR showed by TN *BRCA* mutated patients treated with olaparib²). Using an optimal two-stage Simon model and considering an alpha error of 0.05 and a statistical power of 80%, it will be required to include 31 evaluable patients. Twelve evaluable patients will be enrolled in the first stage, and if at least 4 patients of them have response, additional patients will be recruited to get a total of 31 evaluable patients. Assuming a 10% dropout rate, the total number of patients to be enrolled is 34. Considering, these data the number of responders needed at the end of stage 2 to reject the null hypothesis is at least 14 responders.

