8.2.6.1. Analyses of Primary Endpoint

The primary endpoint is ORR

Objective Response Rate (ORR): A patient will be considered to have achieved an OR if the patient has a sustained complete response (CR) or partial response (PR) according to RECIST v.1.1 definitions. Otherwise, the patient will be considered as non-responders in the ORR analysis. ORR will be estimated by dividing the number of patients with objective response (CR or PR) by the Efficacy population ("response rate").

$$\text{Objective Response Rate} = \frac{\text{Number of CRs + PRs}}{\text{Efficacy population}}$$

The ORR will be reported, including a 95% confidence interval.

These analyses will be conducted at a two-sided 0.05 level of significance.

The number of responders needed at the end of stage 2 to reject the null hypothesis is at least 14 responders.

Additional sensitivity analyses will be outlined in the SAP. For the analysis in the ITT population, patients with inadequate data for tumour assessment (e.g., no baseline assessment or no follow-up assessments) will be considered as non-responders in the OR rate analysis.

In addition, the best objective response for each patient will be summarized.

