### 3.1 Sample Size

We have set the null hypothesis (H0) that ORR will be 30% (ORR achieved by TN patients treated with gemcitabine plus carboplatini) versus the alternative hypothesis (H1) that ORR will be 54% (ORR showed by TN *BRCA* mutated patients treated with olaparibii). Using an optimal two-stage Simon model and considering an alpha error of 0.05 and a statistical power of 80%, it will be required to include 31 evaluable patients. Twelve evaluable patients will be enrolled in the first

stage, and if at least 4 patients of them have response, additional patients will be recruited to get a total of 31 evaluable patients. Assuming a 10% dropout rate, the total number of patients to be enrolled is 34. Considering, these data the number of responders needed at the end of stage 2 to reject the null hypothesis is at least 14 responders.

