## 8. INTERIM ANALYSIS

There is no planned any interim analysis.

The optimal two stage Simon Model is carried out in two steps. The purposes of the step 1 analysis are to allow early stopping of the study for futility.

Following the two-stage Simon design, it will be reviewed whether if at least 4 of the first 12 evaluable patients show tumour response according to RECIST version 1.1, and if this occurs,

additional patients will be included to get a total of 34 patients. If 3 or less patients of the first 12 evaluable patients show an OR, recruitment will be stopped.

In case of recruitment is stopped after the step 1, it will be reviewed the feasibility and interest of performing some of the described secondary and exploratory analysis based on the available number of patients and samples.

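### ORR is reported as a simple proportion with a fixed-sample interval although the two-stage design makes the sample size random; a design-adjusted estimate should be prespecified beside it

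*SAP*

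**What the plan says.** The design is sequential. Protocol 8.1.1 sets stage 1: "Twelve evaluable patients will be enrolled in the first stage, and if at least 4 patients of them have response", recruitment goes on to 31 evaluable patients. SAP 8 gives the other branch: "If 3 or less patients of the first 12 evaluable patients show an OR, recruitment will be stopped". SAP 7.3 adds that, after a stage 1 stop, the database is closed and the primary analysis is run on what is there.

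The estimation plan does not refer to this. SAP 9.2.1.1 takes responders over the Efficacy population and continues: "The ORR will be reported, including a 95% confidence interval using the Clopper-Pearson method (5"). Protocol 8.2.6.1 says only: "The ORR will be reported, including a 95% confidence interval". Both sections fix success as a count of at least 14 responders at the end of stage 2. The general methods in SAP 9.1 and 9.2 name no estimator, p-value or interval that allows for the stopping rule.

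**The concern.** A simple proportion is unbiased, and a Clopper-Pearson interval has its guaranteed coverage, when the sample size is fixed in advance. Here low stage 1 results are frozen at 12 patients, while better ones are diluted by 19 further patients. Low early results therefore keep their full weight and high ones are pulled back toward the truth, so the average over all possible trials falls below the true ORR.

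ORR is the only primary endpoint and the natural planning value for a later study. Near the boundary the choice of estimator moves the result by 2 to 3 points. If it is not prespecified, a choice made after seeing 13 or 14 responders would be open to question.

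**Working it through.** **Inputs (SAP 3.1, SAP 8, Protocol 8.1.1).** Null ORR 30%, alternative 54%, alpha 0.05, power 80%; n1 = 12, continue at 4 or more responders, N = 31, reject at 14 or more.

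**The plan's own figures.** An exact search over Simon two-stage designs at one-sided 0.05 and 80% power returns n1 = 12, N = 31 and rejection at 14 or more as the optimal design, so these three figures reproduce. The stage 1 boundary from the search is one responder stricter than the plan's. That is a separate matter, and everything below uses the plan's rule. Under that rule the probability of rejection is 0.0503 at 30% and 0.861 at 54%.

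**Expected simple proportion.** With X1 the stage 1 responders,

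`E = E[X1; X1<=3]/12 + (E[X1; X1>=4] + 19·p·P(X1>=4))/31`

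- p = 0.30: 1.1259/12 + (2.4741 + 19 × 0.30 × 0.5075)/31 = 0.0938 + 0.1731 = 0.267, bias −3.3 points.
- p = 0.40: 0.5708/12 + (4.2292 + 19 × 0.40 × 0.7747)/31 = 0.0476 + 0.3263 = 0.374, bias −2.6 points.
- p = 0.54: 0.1134/12 + (6.3666 + 19 × 0.54 × 0.9585)/31 = 0.0095 + 0.5226 = 0.532, bias −0.8 points.

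On a fine grid the largest bias is −3.31 points, at p = 0.308.

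**Given continuation.** Divide the second term by P(X1>=4). At p = 0.30 this is 0.1731/0.5075 = 0.341, or +4.1 points. At p = 0.54 it is 0.5226/0.9585 = 0.545, or +0.5 points.

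**Unbiased estimate.** After a stage 1 stop the UMVUE is x/12, so nothing changes. After stage 2 with total s,

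`UMVUE(s) = Σ C(11,x−1)·C(19,s−x) / Σ C(12,x)·C(19,s−x)`, summed over x from 4 to 12.

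For s = 14 this is 115,021,440 / 244,891,665 = 47.0%, against 14/31 = 45.2%.

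| Total | Simple | UMVUE |
|---|---|---|
| 10/31 | 32.3% | 39.2% |
| 12/31 | 38.7% | 42.6% |
| 13/31 | 41.9% | 44.7% |
| 14/31 | 45.2% | 47.0% |
| 17/31 | 54.8% | 55.2% |

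**Behaviour of the two estimators** (RMSE is root mean squared error over all trials, in points):

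| True ORR | P(continue) | Mean simple, all trials | Mean simple, continuing | Mean UMVUE, continuing | RMSE simple | RMSE UMVUE |
|---|---|---|---|---|---|---|
| 30% | 50.7% | 26.7% | 34.1% | 40.6% | 10.8 | 12.1 |
| 40% | 77.5% | 37.4% | 42.1% | 45.5% | 11.9 | 11.6 |
| 54% | 95.9% | 53.2% | 54.5% | 55.3% | 10.6 | 10.0 |

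The mean of the UMVUE over all trials equals the true ORR in each row.

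**Interval.** At 14/31 Clopper-Pearson gives 27.3–64.0%. The two-stage limits solve P(continue and S>=14 | p) = 0.025 and 1 − P(continue and S>=15 | p) = 0.025, giving 27.5–64.6%. Clopper-Pearson coverage under the two-stage distribution (using n = 12 or 31 as it falls) is 96.3% at p = 0.30 and 96.7% at p = 0.54, with a minimum of about 94.0% near p = 0.58.

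**p-value.** Neither document names one for ORR. At 14/31 a one-sided single-stage binomial test would give 0.0534; the two-stage distribution gives 0.0503.

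**The case against.** The strongest reply is that the downward bias is an average that includes trials stopped at 12. A trial that continues is biased upward with the simple proportion, and more so with the UMVUE: 40.6% against 34.1% at a true 30%. All of the UMVUE's correction falls on continuing trials, and it goes upward. At a true 30% it also has the larger RMSE, and at very low totals it reads oddly: 4/31, observed 12.9%, becomes 33.3%. All of this stands. It means the UMVUE should not replace the simple proportion as the sole headline figure. It does not remove the case for showing both, since the UMVUE has no bias over all trials and the smaller RMSE at true rates of 40% and 54%.

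The second reply is that the effect is small where the design is aimed: 0.8 points at 54%, against a Clopper-Pearson interval about 37 points wide at 14/31. That also stands, and it limits the weight of the point.

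A reader might infer three stronger things, none of which the documents support:

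- **That a trial which only just continues or succeeds will on average understate the true ORR.** Given continuation the bias is upward.
- **That the Clopper-Pearson interval is invalid here.** Its coverage stays close to 95%.
- **That the success decision or its error rate is compromised.** The decision is a responder count, and no estimator changes it. Nor would a two-stage interval reconcile a 95% interval with that rule: at 14/31 both lower limits lie below 30%, which reflects a one-sided design paired with two-sided reporting and is a different issue.

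**Conclusion.** The point holds as a modest reporting matter. The simple proportion ignores the stopping rule and, over all trials, is biased low by at most about 3.3 points near 30%, 2.6 at 40% and 0.8 at 54%. Given continuation the bias reverses, to +4.1 points at 30% and +0.5 at 54%. At the success boundary the two estimates differ by 1.8 points (45.2% and 47.0%), and the intervals nearly coincide. Go/no-go, type I error and power are untouched.

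These figures assume exactly 12 and 31 evaluable patients, the stated rule of continuing at 4 or more, and independent responses with a common rate. If all 34 enrolled patients were in the final denominator, the maximum downward bias would be about 3.5 points.

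**What to change.** In SAP 9.2.1.1 and Protocol 8.2.6.1, prespecify that the UMVUE for the two-stage design, with a 95% confidence interval from the two-stage outcome ordering (Jung-Kim or Koyama-Chen), is reported beside the simple proportion with Clopper-Pearson. Any p-value for ORR should come from the same two-stage ordering.

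The cost is one SAP sentence, the matching protocol wording and a few lines of code, with no operational change. SAP 1 requires an amendment for major modifications of the primary analysis, so the sponsor should record whether this addition counts as one. The downside is having two estimates to present. Because the UMVUE sits well above the simple proportion when a trial continues and ends with a low total, both should always be shown, with a line explaining why they differ.

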8.2. Statistical and Analytical Plans

8.2.1. General Considerations

Statistical analysis of this study will be the responsibility of GEICAM. The interpretation of study results will be the responsibility of the Chief Investigator of the study.

Detailed methodology for summary and statistical analyses of the data collected in this study will be documented in a Statistical Analysis Plan (SAP), which will be dated and maintained by GEICAM. This document may modify the plans outlined in the protocol; however, any major modifications of the primary endpoint definition and/or its analysis will also be reflected in a protocol amendment.

All analysis will be performed using the SAS Enterprise Guide 5.1 version.

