# **9. STATISTICAL METHODS ANNALYSES**

## **9.1 Statistical Methods**

For descriptive analyses, frequencies, percentages and ninety-five percent confidence intervals of interest will be calculated for categorical variables wherever possible. For continuous variables, standard descriptive statistics, such as total number of observations, number of available data, mean, standard deviation, minimum, percentile 25, median, percentile 75 and maximum will be calculated.

For efficacy analyses the 2-sided 95% confidence interval will be presented wherever possible. A bilateral (2-sided) 5% significance level will be used to assess the statistical significance.

Chi-square  $\chi^2$  test or Fisher exact test will be used to explore the relationship between two qualitative variables. Mann-Whitney-Wilcoxon test will be used to compare a quantitative variable in two independent groups.

Logistic regression models will be used to test the association of co-variables with a binary variable (ORR, CBR) and to estimate odds ratios and their 95% confidence intervals.

Kaplan-Meier Method will be used to estimate the survival function, survival median and probabilities of occurrence of event at a certain point of time.

Cox Proportional Hazards Regression Model will be used to estimate the hazard ratio and assess the association between several risk factors, considered simultaneously, and survival time (PFS, RD, OS).

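### The primary ORR test is labelled two-sided 0.05, but 12 then 31 patients with rejection at 14 or more responders fits only a one-sided 0.05 Simon design; at exactly 14/31 the label and the responder rule disagree

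*SAP*

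**What the plan says.** The hypotheses and design are in Protocol 8.1.1 and SAP 3.1. The null is set first ("We have set the null hypothesis (H0) that ORR will be 30" percent), the alternative is 54%, and the design is an optimal two-stage Simon design: "considering an alpha error of 0.05 and a statistical power of 80%, it will be required to include 31 evaluable patients". Neither section says whether that alpha is one- or two-sided. Stage 1 has 12 evaluable patients and the trial continues with 4 or more responders. SAP section 8 gives the mirror image: "If 3 or less patients of the first 12 evaluable patients show an OR, recruitment will be stopped".

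The level is declared in the analysis sections. Protocol 8.2.6.1 and SAP 9.2.1.1 both state "These analyses will be conducted at a two-sided 0.05 level of significance", followed immediately by "The number of responders needed at the end of stage 2 to reject the null hypothesis is at least 14 responders". SAP 9.1 applies the same level to efficacy in general: "A bilateral (2-sided) 5% significance level will be used to assess the statistical significance". On estimation, SAP 9.2.1.1 adds "The ORR will be reported, including a 95% confidence interval using the Clopper-Pearson method".

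No section calls the primary test one-sided.

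**The concern.** A Simon design controls the upper-tail error only: the chance of declaring activity when the true ORR is 30%. A two-sided 0.05 test leaves 0.025 in that tail. If the cut-off of 14 was derived with 0.05 in the upper tail, the plan declares an error level about half of what its own rule delivers.

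The responder count is the only criterion tied to rejecting the null, and the confidence interval is only reported. So this is a wrong statement of level, not two competing decision rules. It matters at the boundary, where a report could claim success at two-sided 0.05 next to a pre-specified 95% interval that contains the null value.

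**Working it through.** **Inputs.** Null 0.30, alternative 0.54, power 80%, 12 then 31 evaluable, continue at 4 or more of 12, reject at 14 or more (Protocol 8.1.1; SAP 3.1, 8 and 9.2.1.1). Declared level two-sided 0.05 (Protocol 8.2.6.1; SAP 9.1 and 9.2.1.1). Interval 95% Clopper-Pearson (SAP 9.2.1.1).

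**Formula.** With X1 ~ Bin(12, p) and X2 ~ Bin(19, p), and continuation at c or more in stage 1,

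P(reject | p) = Σ over x from c to 12 of P(X1 = x) · P(X2 ≥ 14 − x).

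This is the type I error at p = 0.30 and the power at p = 0.54.

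**Step 1: reproduce the design.** A search over all two-stage designs for the smallest expected sample size under the null, with power of at least 80%, gives:

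| Upper-tail limit | Stage 1 | Total | Reject at | Error | Power |
|---|---|---|---|---|---|
| 0.05 | 12, stop at ≤4 | 31 | ≥14 | 0.0428 | 0.807 |
| 0.025 | 10, stop at ≤3 | 37 | ≥17 | 0.0243 | 0.804 |

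The stage 1 size, the total and the final cut-off match the documents at 0.05 one-sided and not at 0.025. The fourth number does not match: the reproduced design continues at 5 or more of 12, while the documents continue at 4 or more.

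**Step 2: operating characteristics with 31 evaluable patients.**

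| Continue at | Reject at | Error | Power |
|---|---|---|---|
| ≥4 (as written) | ≥14 | 0.0503 | 0.861 |
| ≥5 (reproduced) | ≥14 | 0.0428 | 0.807 |
| ≥4 (as written) | ≥15 | 0.0231 | 0.780 |
| ≥5 (reproduced) | ≥15 | 0.0206 | 0.741 |

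The two error figures for the cut-off of 14 differ by the single term X1 = 4: P(X1 = 4) · P(X2 ≥ 10) = 0.2311 × 0.0326 = 0.0075, and 0.0428 + 0.0075 = 0.0503. As written, the upper-tail error is 0.0503 / 0.025 = 2.0 times what a two-sided 0.05 test allows.

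**Step 3: where the label and the count disagree (31 evaluable, null 30%).**

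| Responders | 95% Clopper-Pearson | Exact two-sided p (minimum likelihood; doubled tail) | Count rule |
|---|---|---|---|
| 13 | 24.5% to 60.9% | 0.170; 0.214 | does not reject |
| 14 | 27.3% to 64.0% | 0.077; 0.107 | rejects |
| 15 | 30.2% to 66.9% | 0.031; 0.048 | rejects |

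The disagreement is confined to 14.

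**Step 4: how often that happens.** The probability of continuing under the written rule and finishing at exactly 14/31 is P(reject at ≥14) − P(reject at ≥15). At 54% this is 0.8612 − 0.7800 = 0.0812.

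| True ORR | 30% | 40% | 45% | 50% | 54% |
|---|---|---|---|---|---|
| P(exactly 14/31) | 2.7% | 11.1% | 13.2% | 11.4% | 8.1% |

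**Step 5: other evaluable totals.** With the cut-off kept at 14, 32 evaluable patients give an error of 0.0644 (continue at ≥4) or 0.0533 (continue at ≥5). The interval then includes 30% at both 14 and 15 responders (lower limits 26.4% and 29.1%). At 28 evaluable the lower limit for 14 responders is 30.65%, so count and interval agree there and at smaller totals.

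**The case against.** The strongest reply is that nothing in the trial's decision changes. The cut-off of 14 is stated consistently, it is the only criterion linked to rejecting the null, and one-sided testing is normal for a Simon design. The two-sided sentence directly follows the confidence interval, and near-identical wording covers the secondary endpoints, which in those sections have estimates, intervals and curves but no test. It may be boilerplate meant for the interval. The conflict also touches one count at 31 patients, and the design assumptions give it probability 2.7% or 8.1%; the larger figures belong to true rates that the plan does not assume. Finally, relabelling the test one-sided is not enough, because the written stage 1 rule gives 0.0503.

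Much of this stands. The count does govern, the scope is narrow, and the relabelling depends on the stage 1 correction. The interval-only reading does not stand. The sentence speaks of a significance level and sits directly before the rejection rule, and SAP 9.1 uses the two-sided 5% level expressly for judging significance. Even if it meant only the interval, that interval contains 30% at 14/31. That one-sided testing is customary supports correcting a text that says the opposite.

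**Conclusion.** The concern holds. The plan declares two-sided 0.05 for a rule whose upper-tail error is 0.0503 as written, or 0.0428 with the stage 1 boundary of the reproduced design. Neither meets 0.025. With 31 evaluable patients the consequence is one discordant result, 14/31, with probability 8.1% at the design alternative and up to 13.2% among the true rates examined. Enforcing the declared level would raise the cut-off to 15 and lower power to 78.0% under the written stage 1 rule (74.1% if continuation needs 5), below the stated 80%.

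These figures assume exactly 31 evaluable patients, 12 of them in stage 1, and independent responses with a common rate. The point should be fixed. It affects the stated error level of the primary claim, not the sample size or the cut-off.

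**What to change.** Replace the two-sided sentence in Protocol 8.2.6.1 and SAP 9.2.1.1 with: *The primary hypothesis is tested by the Simon responder-count boundary for 31 evaluable patients at a one-sided 0.05 level; the count rule governs the decision. The 95% Clopper-Pearson interval is descriptive.* Exempt the primary test from the two-sided statement in SAP 9.1.

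Make the change together with the stage 1 reconciliation. If continuation stays at 4 of 12, one-sided 0.05 is still marginally exceeded; at 5 of 12 it is met.

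Optionally, report a p-value and 90% interval that respect the two stages. Solving P(reject at ≥14 | p) = 0.05 for p gives a lower limit at 14/31 of 30.6% when continuation needs 5 (p-value 0.043), and 29.97% when it needs 4 (p-value 0.0503).

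The cost is one sentence in each document and one exemption in SAP 9.1. Protocol 8.2.1 (General Considerations) says that "any major modifications of the primary endpoint definition and/or its analysis will also be reflected in a protocol amendment", so a short amendment may be needed. A one-sided 5% level will read as less strict than the current label, but it describes the rule the design was built on. The sample size does not change, and a 14/31 result would still appear beside an interval containing 30%, now with the reason stated in advance.

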#### **9.2.1.2 Analysis of Secondary Endpoints**

The secondary efficacy endpoints are:

**Clinical Benefit Rate (CBR):** A patient will be considered to have CB if the patient has a sustained complete response (CR) or partial response (PR), or stable disease (SD)  $\geq 24$  weeks according to RECIST version 1.1 definitions. Otherwise, the patient will be considered as not achieving CB in the CBR analysis.

CBR will be estimated by dividing the number of patients with CR, PR, or SD  $\geq 24$  weeks by the efficacy population.

$$\text{Clinical Benefit Rate} = \frac{\text{Number of CRs + PRs + SD} \geq 24 \text{ weeks}}{\text{Efficacy Population}}$$

The CBR will be reported, including a 95% confidence interval.

For the CBR analysis in the ITT population, patients with inadequate data for tumour assessment (e.g., no baseline assessment or no follow-up assessments) will be considered as not achieving CB in the CBR analysis.

**Duration of Response (DoR):** DoR is defined as the time from the first documentation of objective tumour response (CR or PR) to the first documented PD using RECIST version 1.1, or to death due to any cause, whichever occurs first. DoR data will be censored on the date of the last tumour assessment on study for patients who do not have objective PD and who have not died due to any cause while on study. Additionally, patients who start a new anti-cancer therapy prior to documented PD will be censored at the date of the last tumour assessment prior to the start of the new therapy.

RD will only be calculated for the subgroup of patients with an objective response.

**Progression-Free survival (PFS):** PFS is defined as the time from study enrolment to the first documented PD, using RECIST version 1.1, or death from any cause, whichever occurs first. PFS data will be censored on the date of the last tumour assessment on study for patients who do not have objective PD and who have not died due to any cause while on study. Additionally, patients who start a new anti-cancer therapy prior to documented PD will be censored at the date of the last tumour assessment prior to the start of the new therapy.

The analyses of PFS will be performed in the ITT and Efficacy populations. PFS time will be summarized for the ITT population using the Life tables and displayed graphically where appropriate. Confidence intervals (CIs) for the 25th, 50th and 75th percentiles of the event free time will be reported.

**Overall Survival (OS):** OS is defined as the time from the date of study enrolment to the date of death from any cause. OS data will be censored on the last date the patient is known to be alive.

OS will be analysed in the ITT and Efficacy population. The median event times and 95% CIs will be estimated.

All of the above secondary analyses will be conducted at a two-sided 0.05 level of significance.

The secondary time-to-event endpoints (RD, PFS, OS) will be summarised using a Kaplan-Meier analysis and associated curves.

